### **7.4 Liver safety monitoring**

To ensure patient safety and enhance reliability in determining the hepatotoxic potential of an investigational drug, a standardized process for identification, monitoring and evaluation of liver events has to be followed.

The following two categories of abnormalities / adverse events have to be considered during the course of the study (irrespective of whether classified/reported as (S)AE):

- Liver laboratory triggers, which will require repeated assessments of the abnormal laboratory parameter
- Liver events, which will require close observation, follow-up monitoring and completion of the standard base liver CRF pages

Please refer to [Table 13-1 in Appendix 2](#) for complete definitions of liver laboratory triggers and liver events.

Every liver laboratory trigger or liver event as defined in [Table 13-1 of Appendix 2](#) should be followed up by the investigator or designated personal at the trial site as summarized below. Detailed information is outlined in [Table 13-2 in Appendix 2](#).

For the liver laboratory trigger:

- Repeating the liver function test (LFT) within the next week to confirm elevation.

These LFT repeats must be performed using the central laboratory if possible. If this is not possible, then the repeats can be performed at a local laboratory to monitor the safety of the patient. Repeats laboratory must then be performed at central laboratory as soon as possible. If a liver event is subsequently reported, any local LFTs previously conducted that are associated with this event must be reported on the Liver CRF pages.

- If the elevation is confirmed, close observation of the patient will be initiated, including consideration of treatment interruption if deemed appropriate.

For the liver events:

- Repeating the LFT to confirm elevation as appropriate
- Discontinuation of the investigational drug if appropriate
- Hospitalization of the patient if appropriate
- A causality assessment of the liver event via exclusion of alternative causes (e.g., disease, co-medications)
- An investigation of the liver event which needs to be followed until resolution.

These investigations can include serology tests, imaging and pathology assessments, hepatologist's consultancy, based on investigator's discretion. All follow-up information, and the procedures performed must be recorded on appropriate CRF pages, including the liver event overview CRF pages.

## 7.5 Reporting of study treatment errors including misuse/abuse

Medication errors are unintentional errors in the prescribing, dispensing, administration or monitoring of a medicine while under the control of a healthcare professional, patient or consumer (EMA definition).

Misuse refers to situations where the medicinal product is intentionally and inappropriately used not in accordance with the protocol.

Abuse corresponds to the persistent or sporadic, intentional excessive use of a medicinal product, which is accompanied by harmful physical or psychological effects.

Study treatment errors and uses outside of what is foreseen in the protocol will be collected in the DAR (dose administration record) eCRF irrespective of whether or not associated with an AE/SAE and reported to Safety only if associated with an SAE. Misuse or abuse will be collected and reported in the safety database irrespective of it being associated with an AE/SAE.

**Table 7-1 Guidance for capturing the study treatment errors including misuse/abuse**

Treatment error type	Document in Dose Administration (DAR) eCRF (Yes/No)	Document in AE eCRF	Complete SAE form
Unintentional study treatment error	Yes	Only if associated with an AE	Only if associated with an SAE
Misuse/Abuse	Yes	Yes	Yes, even if not associated with a SAE

## **7.6 Pregnancy reporting**

To ensure patient safety, each pregnancy occurring after signing the informed consent must be reported to Novartis within 24 hours of learning of its occurrence. The pregnancy should be followed up to 3 months after the birth, including spontaneous or voluntary termination, details of the birth, and the presence or absence of any birth defects, congenital abnormalities, or maternal and/or newborn complications.

Pregnancy must be recorded on the Pharmacovigilance Pregnancy Form and reported by the investigator to the local Novartis Drug Safety and Epidemiology Department. Pregnancy follow-up should be recorded on the same form and should include an assessment of the possible relationship to the study treatment.

Any SAE experienced during the pregnancy and unrelated to the pregnancy must be reported on a SAE form.

## **8 Data review and database management**

### **8.1 Site monitoring**

Before study initiation, at a site initiation visit or at an investigator's meeting, a Novartis representative will review the protocol and data capture requirements (i.e. eSource or eCRFs) with the investigators and their staff. During the study, Novartis employs several methods of ensuring protocol and GCP compliance and the quality/integrity of the sites' data. The field monitor will visit the site to check the completeness of patient records, the accuracy of data capture / data entry, the adherence to the protocol and to Good Clinical Practice, the progress of enrollment, and to ensure that study treatment is being stored, dispensed, and accounted for according to specifications. Key study personnel must be available to assist the field monitor during these visits. Continuous remote monitoring of each site's data may be performed by a centralized Novartis CRA organization. Additionally, a central analytics organization may analyze data & identify risks & trends for site operational parameters, and provide reports to Novartis Clinical Teams to assist with trial oversight.

The investigator must maintain source documents for each patient in the study, consisting of case and visit notes (hospital or clinic medical records) containing demographic and medical information, laboratory data, electrocardiograms, and the results of any other tests or assessments. All information on CRFs must be traceable to these source documents in the patient's file. The investigator must also keep the original informed consent form signed by the patient (a signed copy is given to the patient).

The investigator must give the monitor access to all relevant source documents to confirm their consistency with the data capture and/or data entry. Novartis monitoring standards require full verification for the presence of informed consent, adherence to the inclusion/exclusion criteria, documentation of SAEs, and of data that will be used for all primary variables. Additional checks of the consistency of the source data with the CRFs are performed according to the study-specific monitoring plan. No information in source documents about the identity of the patients/subjects will be disclosed.

## 8.2 Data collection

Designated investigator staff will enter the data required by the protocol into the OC/RDC system. Designated investigator site staff will not be given access to the system until they have been trained.

Automatic validation procedures within the system check for data discrepancies during and after data entry and, by generating appropriate error messages, allow the data to be confirmed or corrected online by the designated investigator site staff. The Investigator must certify that the data entered into the electronic Case Report Forms are complete and accurate. After database lock, the investigator will receive copies of the patient data for archiving at the investigational site.

## 8.3 Database management and quality control

Novartis staff review the data entered into the CRFs by investigational staff for completeness and accuracy and instruct the site personnel to make any required corrections or additions. Queries are sent to the investigational site using an electronic data query. Designated investigator site staff is required to respond to the query and confirm or correct the data. If the electronic query system is not used, a paper Data Query Form will be faxed to the site. Site personnel will complete and sign the faxed copy and fax it back to Novartis staff that will make the correction to the database. The signed copy of the Data Query Form is kept at the investigator site.

Concomitant medications entered into the database will be coded using the WHO Drug Reference List, which employs the Anatomical Therapeutic Chemical classification system. Concomitant procedures, non-drug therapies and adverse events will be coded using the Medical dictionary for regulatory activities (MedDRA) terminology.

Laboratory samples will be processed centrally and the results will be sent electronically to Novartis.

ECG readings will be processed centrally and the results will be sent electronically to Novartis.

Spirometry readings will be processed centrally and the results will be sent electronically to Novartis.

Diary data will be entered into an electronic diary by the patient. The system will be supplied by a vendor(s), who will also manage the database. The database will be sent electronically to Novartis personnel.

Data about all study drug(s) dispensed to the patient and all dosage changes will be tracked using an Interactive Response Technology (IRT). The system will be supplied by a Novartis IRT, who will also manage the database. The database will be sent electronically to Novartis.

The occurrence of relevant protocol deviations will be determined. After these actions have been completed and the database has been declared to be complete and accurate, it will be locked and made available for data analysis. Any changes to the database after that time can only be made after written agreement by Novartis Development management.

## **8.4 Data Monitoring Committee**

Not required.

## **8.5 Adjudication Committee**

An independent external adjudication committee will be established to assess serious asthma outcomes (asthma-related hospitalizations, intubations and deaths). All serious asthma outcomes, and deaths occurring from the time of treatment start until the 30 days after the permanent discontinuation of study drug, where applicable, will be adjudicated.

The committee will consist of experts outside Novartis who are not involved in the study conduct, who will periodically review pertinent patient data and the supporting documentation to settle the specified adjudication objectives. Further details will be provided in the Adjudication Committee Charter.

## **9 Data analysis**

The analysis will be conducted on all subject data at the time the trial ends. Any data analysis carried out independently by the investigator should be submitted to Novartis before publication or presentation.

### **9.1 Analysis sets**

The Safety Set will consist of all patients who received at least one dose of study medication during this study.

Full Analysis Set (FAS) will consist of all patients who entered in this study and received at least one dose of study medication during this study.

Note that the Safety Sets and FAS are the same except that the Safety Set allows the inclusion of patients who are not intended to enter in this study but received study drug in error.

The Safety Set will be used in the analysis of all safety variables. The efficacy analysis population will be the FAS.

### **9.2 Patient demographics and other baseline characteristics**

Demographic and baseline characteristics including age, sex, race, ethnicity, height, weight, body mass index (BMI), relevant medical history, screening spirometry parameters: (FEV1, FVC, and FEV1/FVC), FEV1 reversibility, percentage of predicted FEV1, baseline PEF, duration of asthma, history of asthma exacerbations, smoking history, prior concurrent medications (asthma-related and non-asthma-related), vital signs (systolic and diastolic blood pressure, pulse rate), QTc using Fridericia's correction and baseline ACQ-7 will be summarized.

Continuous variables will be summarized using descriptive statistics (mean, median, standard deviation, minimum, and maximum) and categorical variables will be summarized in terms of the number and percentage of patients in each category for the Safety Set.

Baseline is defined as the last measurement before first dose of study drug.

### **9.3 Treatments**

Study drug administration and concomitant medication data will be listed and summarized using the Safety Set.

The duration of exposure and the number of patients who completed the study medication and who discontinued from the study medication will be summarized.

Medications started and stopped prior to study drug, and taken concomitantly will be summarized for the Safety Set.

Concomitant therapies will be recorded, listed and summarized separately for asthma related medications / non-drug therapies and other medications. Concomitant asthma related medications will be summarized by route of administrations, the recorded pre-specified drug subcategories (including type of combinations) and preferred term. Concomitant medications not related to asthma will be summarized by route of administration and preferred term.

SABA usage (number of puffs) during the screening epoch will be summarized.

Treatment compliance with study medication over the study period will be summarized.

### **9.4 Analysis of the primary variable(s)**

#### **9.4.1 Primary Variable(s)**

The primary objective of this study is to assess the safety/tolerability of 52 weeks of treatment with QMF149 (150/320 µg, once daily), particularly with regard to treatment emergent adverse event reporting in Japanese patients with inadequately controlled asthma.

The primary variable is the number and percentage of patients who reported treatment emergent adverse events during the 52 week study period.

Adverse events will be summarized with descriptive statistics for the Safety Set.

All study emergent adverse events including asthma exacerbations will be summarized and listed. Adverse events starting on or after the time of the first inhalation of study drug but not later than 7 days (30 days in the case of a SAE) after the last administration will be classified as a treatment emergent adverse event. Any adverse events that started during the study before the time of the first inhalation of study drug will be classified as a prior adverse event.

#### **9.4.2 Statistical model, hypothesis, and method of analysis**

The number and percentage of patients who reported treatment emergent adverse events will be summarized by primary system organ class, preferred term for

- All adverse events
- Serious adverse events
- Adverse events by maximum severity
- Adverse events suspected to be related to study drug
- Adverse events leading to permanent study drug discontinuation
- Adverse events of special interest

In addition, all adverse events reported in the study will be listed.

### **9.4.3 Handling of missing values/censoring/discontinuations**

No imputation will be done for missing data. All available data will be summarized.

### **9.4.4 Sensitivity analyses**

Not applicable.

## **9.5 Analysis of secondary variables**

### **9.5.1 Efficacy variables**

The efficacy measurements during the study will be summarized for the FAS.

Baseline is defined as the last measurement before first dose of the study drug, unless otherwise specified. No imputation will be done for missing data.

### **Spirometry**

Spirometry measurements taken within 7 days of systemic corticosteroid use and/or 6 hours of rescue use will be set to missing and not be imputed, unless specified otherwise.

For FEV1 and FVC, the baseline is defined as the mean of the values taken in the clinic at 45 and 15 min prior to first dose at Visit 101.

### **Pre-dose FEV1 and FVC at Weeks 12, 26 and 52**

The pre-dose FEV1 is defined as the mean of the pre-dose 45 and 15 min FEV1 values.

The pre-dose FEV1 and the change from baseline at 12, 26 and 52 weeks of the study treatment will be summarized with descriptive statistics. Summaries will be repeated for pre-dose FVC.

In addition, the means in pre-dose FEV1 and FVC for each visit will be displayed graphically.

### **Peak Expiratory Flow Rate (PEF)**

The morning/evening PEF (liters/min) will be averaged over the first 26 weeks and over the 52 weeks.

e-Diary data recorded during the screening period will be used to calculate the baseline value.

The mean morning/evening PEF and the mean change from baseline will be summarized.

### **Rescue medication**

The total number of puffs of rescue medication per day over the first 26 weeks and over the 52 weeks will be calculated and divided by the total number of days to derive the mean daily number of puffs of rescue medication taken for the patient.

e-Diary data recorded during the screening period will be used to calculate the baseline value.

The mean daily number of puffs of rescue medication use over the first 26 weeks and over the 52 weeks of treatment and the mean change from baseline will be summarized.

In addition, the mean number of puffs of rescue medication in the morning and in the evening, and the percentage of 'rescue medication free days' (defined from diary data as any day where the patient did not use any puffs of rescue medication) will be summarized.

### **ACQ-7 at Weeks 26 and 52**

ACQ-7 and the change from baseline at 26 and 52 weeks of the study treatment will be summarized.

The proportion of patients who achieve an improvement of at least 0.5 in ACQ-7 (i.e. decrease of ACQ-7 score of at least 0.5 from baseline) at post-baseline visits will be summarized.

### **9.5.2 Safety variables**

All safety variables will be summarized with descriptive statistics for the Safety Set.

Baseline is defined as the last measurement before first dose of the study drug, unless otherwise specified. No imputation will be done for post-baseline missing data.

#### **Electrocardiogram (ECG) and vital signs**

Data from the ECG (including QT interval, RR interval, PR interval, QRS duration, heart rate, Fridericia's QTc and Bazett's QTc) will be summarized at 30 min pre-dose, and at 30 min post-dose by visit. The baseline measurement will be the 30 min pre-dose measurement at Visit 101.

Vital signs (blood pressure, radial pulse rate) will also be summarized by visit.

The maximum (QTc, systolic blood pressure, radial pulse rate) or minimum (diastolic blood pressure) post first dosing (i.e., post-baseline) value will be summarized. The changes from baseline will also be summarized by visit.

All data will be included in the analysis regardless of rescue medication usage.

The number and percentage of patients by the following classifications will be presented for each visit.

The number (%) of patients with pulse rate of < 40 and > 90 bpm; systolic blood pressure of < 90 and > 140 mmHg; diastolic blood pressure of < 50 and > 90 mmHg will be summarized.

Notable values for vital signs and the change from baseline will be summarized. A notable value is defined as follows:

#### **Systolic blood pressure**

“Low” criterion: < 75 mmHg, or  $\leq 90$  mmHg and decrease from baseline  $\geq 20$  mmHg

“High” criterion: > 200 mmHg, or  $\geq 180$  mmHg and increase from baseline  $\geq 20$  mmHg

#### **Diastolic blood pressure**

“Low” criterion: < 40 mmHg, or  $\leq 50$  mmHg and decrease from baseline  $\geq 15$  mmHg

“High” criterion: > 115 mmHg, or  $\geq 105$  mmHg and increase from baseline  $\geq 15$  mmHg

#### Pulse rate

”Low” criterion:  $< 40$  bpm, or  $\leq 50$  bpm and decrease from baseline  $\geq 15$  bpm

“High” criterion:  $> 130$  bpm, or  $\geq 120$  bpm and increase from baseline  $\geq 15$  bpm

Notable QTc values and the changes from baseline will be summarized. A notable value is defined as a QTc interval of greater than 450 ms (male), 460 ms (female) and 500 ms (both) at baseline and the number of newly occurring or worsening notable QTc values for post baseline time points. The categories used for the change from baseline in QTc are less than 30 ms, 30 to 60 ms and greater than 60 ms.

QTc will be calculated from the QT interval and RR (in seconds) by two methods:

1. using Fridericia's formula:  $QTc = QT / \sqrt[3]{RR}$ , where  $\sqrt[3]{}$  denotes the cube root
2. using Bazett's formula:  $QTc = QT / \sqrt{RR}$

ECG and vital signs data measured more than 7 days after last inhalation of study drug is regarded as post-treatment data and will not be summarized, only listed.

#### **Laboratory data:**

Evening plasma cortisol will be summarized by visit. The maximum evening plasma cortisol post first dosing (i.e. post baseline value) will be summarized. The changes from baseline will also be summarized by visit.

All other laboratory data will be listed with abnormal values flagged. The laboratory values and the change from baseline for continuous laboratory parameters will be summarized at each visit. A frequency table of results for categorical laboratory parameters will be produced by visit. Shift tables relative to the normal reference ranges will be used to summarize the change from baseline to post-baseline by visit for each laboratory parameter.

All data will be included in the analysis regardless of rescue medication usage.

Laboratory data measured more than 7 days after last inhalation of study drug is regarded as post-treatment data and will not be summarized, only listed.

#### **9.5.3 Resource utilization**

Not applicable.

#### **9.5.4 Pharmacokinetics**

Not applicable.

#### **9.5.5 DNA**

Not applicable.

#### **9.5.6 Biomarkers**

Not applicable.

### 9.5.7 PK/PD

Not applicable.

## 9.7 Interim analyses

An interim analysis for 6-month data will be performed for the initial New Drug Application submission in Japan ([Section 3.2](#)). This analysis will be performed after all patients have been enrolled and completed Visit 107 (Week 26) or discontinued the study.

The cut-off date for each patient is defined as the Visit 107 date or study discontinuation date prior to Visit 107. All protocol specified analyses will be performed for all data on or prior to this cut-off date.

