### 5.6.2 Discontinuation of study treatment

Discontinuation of study treatment for a patient occurs when study drug is stopped earlier than the protocol planned duration, and can be initiated by either the patient or the investigator.

Patients may voluntarily discontinue study treatment for any reason at any time. In the case the patients would want to discontinue the treatment, it is particularly important to ask the reason and if they would be willing to remain in the trial to share their safety and vital status information (e.g., via telephone contact) until the scheduled final visit in order to ensure the scientific integrity of the trial.

The investigator must discontinue study treatment for a given patient if, on balance, he/she believes that continuation would negatively impact the risk/benefit of trial participation.

Study treatment must be discontinued under the following circumstances:

- Patient wish
- Adverse events for which continued inhalation of the investigational drug would be detrimental
- Abnormal test procedure results indicating risk for the patient on continued inhalation of the investigational drug
- Pregnancy (see [Section 6.5.7](#) and [Section 7.6](#))
- If a patient develops a medical condition that requires use of prohibited treatment as per [Section 5.5.8](#) or if patient exhibits a behavior of non-compliance regarding prohibited medications
- Patients who experience 5 or more asthma exacerbations during the treatment epoch that required treatment with systemic corticosteroids
- Patients with > 50% decrease in FEV1 from baseline (Visit 101) during treatment epoch
- Any situation in which study participation might result in a safety risk to the patient

If discontinuation of study treatment occurs, the patient should NOT be considered withdrawn from the study. The patient should return to the clinic as soon as possible, after discontinuation of investigational drug, for a study treatment discontinuation visit. If the patient fails to return for the study treatment discontinuation visit for unknown reasons, every

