### **7.2.2 SAE reporting**

To ensure patient safety, every SAE, regardless of causality, occurring after the patient has provided informed consent and until 30 days after the patient has stopped study participation (defined as time of last dose of study drug taken or last visit whichever is later) must be reported to Novartis safety within 24 hours of learning of its occurrence. Any SAEs experienced after the 30 days period should only be reported to Novartis safety if the investigator suspects a causal relationship to study treatment.

All follow-up information for the SAE including information on complications, progression of the initial SAE and recurrent episodes must be reported as follow-up to the original episode within 24 hours of the investigator receiving the follow-up information. An SAE occurring at a different time interval or otherwise considered completely unrelated to a previously reported one must be reported separately as a new event.

Information about all SAEs is collected and recorded on the Serious Adverse Event Report Form; all applicable sections of the form must be completed in order to provide a clinically thorough report. The investigator must assess the relationship of each SAE to *each specific component of study treatment*, complete the SAE Report Form in English, and submit the completed form within 24 hours to Novartis. Detailed instructions regarding the submission process and requirements for signature are to be found in the investigator folder provided to each site.

Follow-up information is submitted as instructed in the investigator folder. Each re-occurrence, complication, or progression of the original event must be reported as a follow-up to that event regardless of when it occurs. The follow-up information should describe whether the event has resolved or continues, if and how it was treated, and whether the patient continued or withdrew from study participation.

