2.5.1 Primary endpoint

The primary variable is the number and percentage of patients who reported treatment emergent adverse events during the 52 week study period for the Safety set.

All treatment emergent adverse events including asthma exacerbations will be summarized and listed. Adverse events starting on or after the time of the first inhalation of study drug but not later than 7 days (30 days in the case of a SAE) after the last administration will be classified as a treatment emergent adverse event. Any adverse events that started during the study before the time of the first inhalation of study drug will be classified as a prior adverse event.

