2.7 Safety analyses

All safety variables will be summarized with descriptive statistics for the Safety Set.

Baseline is defined as the last measurement before first dose of the study drug, unless otherwise specified.

No imputation will be done for post-baseline missing data.

Post-baseline measurements comprise recordings up to the last dose of study drug + 7 days for laboratory, ECG, vital signs, non-serious AE and up to the last dose of study drug + 30 days for SAEs and death.

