2.13 Interim analysis

The cut-off date for each patient is defined as the Visit 107 date or study discontinuation date prior to Visit 107. All protocol specified analyses will be performed for all data on or prior to this cut-off date.

3 Sample size calculation

Since asthma is a chronic disease, and QMF149 is expected to be administered over a long period, safety in long-term treatment needs to be confirmed. “Regarding sample size and treatment period required to assess safety at the clinical study stage of a new drug anticipated to be administered for a non-fatal disease over a long period” (Notification No. 592 of the Pharmaceuticals and Cosmetics Division, Pharmaceutical Affairs Bureau, MHLW, dated 24-May 24, 1995), this notification requires to collect safety data of at least 100 patients who receive the drug over one year. CQVM149B2301 and 2302 study were planned to collect

efficacy and safety data of about 41 Japanese Asthma patients exposed to QMF149. Therefore this study, CQVM149B1305, is designed to obtain safety data of approximately 59 Japanese asthma patients exposed to QMF149. Since a 25% screening failure rate and a 10% dropout rate are expected, approximately 88 patients will need to be screened in order to collect approximately 66 patients who enter the treatment epoch and to collect a total of approximately 59 completed patients.

4 Change to protocol specified analyses

No change from protocol specified analysis is made.

5 Appendix

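### The interim cut-off at Visit 107 has no exception for serious events or deaths, so later ones already collected are left out of the interim analyses used for the first submission

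*Protocol*

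**What the plan says.** Protocol 9.7 gives the purpose: "An interim analysis for 6-month data will be performed for the initial New Drug Application submission in Japan". On timing it says: "This analysis will be performed after all patients have been enrolled and completed Visit 107 (Week 26) or discontinued the study". It then sets the per-patient limit: "The cut-off date for each patient is defined as the Visit 107 date or study discontinuation date prior to Visit 107". SAP 2.13 repeats the rule and its scope: "All protocol specified analyses will be performed for all data on or prior to this cut-off date". Neither text makes an exception for any type of event, and SAP Section 4 declares no departure from the protocol.

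The safety definitions reach further:

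- SAP 2.5.1, like Protocol 9.4.1, counts an event as treatment emergent if it starts on or after the first inhalation and "not later than 7 days (30 days in the case of a SAE) after the last administration".
- SAP 2.7 takes post-baseline safety data "up to the last dose of study drug + 30 days for SAEs and death".
- Protocol 7.2.2 requires sites to report SAEs "until 30 days after the patient has stopped study participation".

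Three other provisions limit the effect. Protocol 5.6.2 separates stopping drug from leaving the study: "If discontinuation of study treatment occurs, the patient should NOT be considered withdrawn from the study". SAP 2.7.1.1 lists every death in the database and puts the 30-day limit only on the summary tables. Protocol Section 9 and SAP 2.1 say that the end-of-trial analysis uses all subject data.

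**The concern.** The study exists to provide long-term safety data, and its interim goes into the first submission. The interim starts only when the last patient has reached Week 26 or left, so patients enrolled earlier will already have been on drug for longer. An SAE in one of them after Visit 107 is treatment emergent by the plan's definition and has been collected, yet it falls outside all interim analyses. The same holds for a patient who leaves the study before Week 26 and has an SAE within 30 days of the last dose.

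With 66 patients and few serious events expected, one or two missing SAEs could change how the interim safety picture reads. The usual reasons for holding back later data do not apply: the study is open-label, single-arm and descriptive, with no hypothesis test to protect.

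SAP 2.5.2 also asks for adverse events by time of onset, with a category beyond 26 weeks. Under the cut-off, that category would be essentially empty at the interim even where such events are known.

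**Working it through.** **The plan's own figures.** The interim rule states no number. The sample size (Protocol 9.8, SAP 3) reproduces: 100 − 41 = 59 completers; 59/0.90 = 65.6, so 66 entering treatment; 66/0.75 = 88 screened.

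**The rule applied to four cases** (Visit 107 taken as Day 183):

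| Case | Treatment emergent by SAP 2.5.1? | In the interim? |
|---|---|---|
| Still on drug, SAE on Day 220, in the database when the last patient reaches Week 26 | Yes | No |
| Last dose and study exit on Day 100, SAE on Day 115 | Yes (15 days after last dose) | No |
| Last dose on Day 100, stays in the study, SAE on Day 115 | Yes | Yes, the cut-off is still Visit 107 |
| Last dose on Day 170, stays in the study, SAE on Day 190 | Yes (20 days after last dose) | No |

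**Data after Visit 107.** Assume uniform enrolment over E weeks and ignore any lag from the last Visit 107 to the database cut-off. Mean extra follow-up is the mean of min(U, 26) with U uniform on 0 to E. The share dropped is extra/(26 + extra).

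As a check with dropout, take a constant hazard λ = −ln(0.9)/52 per week, from the plan's 10% dropout. Interim exposure is 66 × (1 − e^(−26λ))/λ/52 = 32.1 patient-years. Excluded exposure is 66 × e^(−26λ) × mean[(1 − e^(−λx))/λ]/52, with x = min(U, 26).

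| Assumed enrolment | Mean extra weeks | Share dropped, no dropout | Patient-years dropped, with dropout | Share dropped, with dropout |
|---|---|---|---|---|
| 3 months (13 weeks) | 6.5 | 6.5/32.5 = 20% | 7.8 | 7.8/39.9 = 20% |
| 6 months (26 weeks) | 13.0 | 13.0/39.0 = 33% | 15.4 | 15.4/47.5 = 32% |
| 9 months (39 weeks) | 17.3 | 17.3/43.3 = 40% | 20.4 | 20.4/52.5 = 39% |

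The documents give no SAE rate. At an assumed 0.03 to 0.15 per patient-year, the SAEs left out number between 7.8 × 0.03 = 0.2 and 20.4 × 0.15 = 3.1. Those included number between 32.1 × 0.03 = 1.0 and 32.1 × 0.15 = 4.8.

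**Patients who leave the study before Visit 107.** The expected number is 66 × (1 − 0.9^0.5) = 3.4 under constant hazard. If all dropout came early it would be 66 × 0.10 = 6.6. If each leaver loses the full 30 days, the loss is 3.4 × 30/365.25 = 0.28 to 6.6 × 30/365.25 = 0.54 patient-years. Against 32.1 that is 0.9% to 1.7%. This is an upper bound, because it treats every dropout as leaving the study on the day of the last dose.

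**Patients who stop drug in the 30 days before Visit 107.** The expected number is 66 × (e^(−λ(26 − 30/7)) − e^(−26λ)) = 0.5.

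**The case against.** The strongest defence is that this is a 6-month analysis by design. The primary variable is a crude percentage of patients with events, which is hard to interpret if follow-up runs from 26 to nearly 52 weeks. That stands: the Visit 107 cut is a legitimate choice for the incidence tables as well as for by-visit and efficacy summaries. It does not explain why nothing supplementary shows later serious events already in hand.

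A reader might infer that the rule cuts off patients who stop drug because of an adverse event, the group most likely to have further events. The documents do not support that. Such patients stay in the study, have a safety call 30 days after discontinuation and further calls at scheduled visits (Protocol 5.6.2, Table 5-4), and keep their full window unless they stop within 30 days of Visit 107. Study leavers are a different and smaller group. After withdrawal of consent, Protocol 5.6.3 allows no further assessments and restricts contact, so some of the missing window data will never exist.

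A reader might also infer that late deaths vanish from every interim output. That is not established, because the SAP 2.7.1.1 listing may already show them. The SAP does not say whether that listing or the cut-off prevails at the interim, and the listing does not cover non-fatal SAEs or adverse events leading to discontinuation.

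Nothing is lost for good. The final analysis takes all data, and SAEs go to the sponsor within 24 hours (Protocol 7.2.2). Protocol 9.7 also refers to Section 3.2, where part of the text is not visible, so an agreed interim scope may be recorded there.

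**Conclusion.** The point holds as a gap in the interim only. As written, the cut-off excludes collected SAEs and other adverse events that the plan itself calls treatment emergent, and it keeps deaths after the cut-off out of the interim summaries.

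The part that matters is follow-up after Visit 107: about 20% to 40% of accrued patient-time for enrolment of 3 to 9 months, or roughly 0.2 to 3.1 SAEs. Accrual time and SAE rate are both assumptions. The part that comes from cutting the 7/30-day windows is small: about 3 study leavers expected and about 7 at most, no more than 1% to 2% of interim exposure, plus about half a patient who stops drug shortly before Visit 107.

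It would go too far to say that the interim is invalid, that the 6-month cut is wrong, or that safety data are suppressed. The change is a cheap improvement that makes the interim safety picture more complete.

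**What to change.** Amend Protocol 9.7 and SAP 2.13 as follows:

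1. Keep the Visit 107 cut for by-visit, efficacy and 6-month incidence tables.
2. For patients who stopped drug or left the study by Visit 107, include collected AEs within 7 days and SAEs and deaths within 30 days of the last dose, up to the interim database cut-off.
3. Add a supplementary listing and count of all SAEs, deaths and adverse events leading to discontinuation up to one common interim database cut-off date, marking those after Visit 107.
4. State that the SAP 2.7.1.1 listing of all deaths applies at the interim.

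The cost is a few sentences and a few extra interim outputs. No added data collection is needed, and no error rate or blinding is at stake. The supplementary count covers unequal follow-up, so it should be shown with the patient-years behind it and kept apart from the 6-month percentages.
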